Central blinded raters will be used to rate Parts 3 and 4 of the UDysRS, the primary efficacy endpoint for this study. Assessment obtained at V3 will serve as the baseline for clinical assessment. The scales will also be performed at Weeks 2, 4, 8, and 12. The scoring for Parts 3 and 4 are to be performed by a trained central blinded rater who will not have access to the results of other study assessments or medical records for the subject and who will not participate in the care or management of the subject.

Section 5.5.7 Drug Accountability Third paragraph, second sentence previously read:

This will be documented by the Investigator signing and dating the Proof of Receipt (POR) after he/she receives LCIG from the depot for the initial supplies, and by signing the POR upon receipt of LCIG from the depot.

Has been changed to read:

This will be documented by the Investigator or designee signing and dating the Proof of Receipt (POR) after he/she receives LCIG from the depot for the initial supplies, and by signing the POR upon receipt of LCIG from the depot.

Section 5.6.2 Appropriateness of Measurements Subsection UDysRS Validation and Psychometric Properties First paragraph, last sentence previously read:

Convergent, content and discriminant validity have also not been assessed.

Has been changed to read:

Convergent and discriminant validity have also not been assessed.

Section 5.6.2 Appropriateness of Measurements
Subsection UDysRS Validation and Psychometric Properties
Last paragraph previously read:

In conclusion, the UDysRS is a comprehensive rating tool to measure dyskinesia and has been studied clinimetrically as both a consistent and reliable measure. The scale however has not been assessed for construct and content validity.

Has been changed to read:

[figure not shown]
The UDysRS is a comprehensive rating tool to measure dyskinesia and has been studied clinimetrically as both a consistent and reliable measure. The scale however has not been assessed for construct and content validity.

Additional analysis will be performed to provide evidence on the construct validity of the UDysRS. Convergent validity will be evaluated by Spearman rank correlations between UDysRS total score (and sub-scores) and the AIMS score and Parkinson's Disease Diary assessment of severity of dyskinesia. In addition, the association with indirectly related constructs to dyskinesia, the PDQ-8 total score (measuring the PD-specific health status and quality of life) as well as the UPDRS scores for Parts II – III will be determined. Correlations ≥ 0.30 are hypothesized to support convergent validity. Discriminative validity will be explored by sub-group analyses. The UDysRS total score will be stratified by the Hoehn and Yahr stages and tested using the Kruskal-Wallis test.

abbyie Levodopa-Carbidopa Intestinal Gel/Carbidopa Levodopa Enteral Suspension M15-535 Protocol Amendment 1 EudraCT 2016-001403-23

Section 7.0 Protocol Deviations Contact information previously read:

Section 8.1.3.3 Additional Efficacy and Health Outcomes Analyses First paragraph, first bullet previously read:

"ON" time without troublesome dyskinesia and "ON" time without dyskinesia as measured by the PD Diary

Has been changed to read:

• UDysRS Historical Score, Objective Score and Parts 1 through 4 Scores

"ON" time with troublesome dyskinesia and "ON" time without dyskinesia as measured by the PD Diary

Section 8.1.3.3 Additional Efficacy and Health Outcomes Analyses Last paragraph, last sentence previously read:

To evaluate this assumption, the MMRM analysis of the primary and secondary variables will be repeated using only subjects who completed the planned treatment period.

Has been changed to read:

To evaluate this assumption, the MMRM analysis of the primary and secondary variables will be repeated using only subjects who completed the planned treatment period and additional sensitivity analyses to evaluate the impact of missing data on the primary efficacy results will be performed. These sensitivity analyses will be described in the Statistical Analysis Plan (SAP).

Section 9.3 Subject Information and Consent First paragraph, first sentence previously read:

The Investigator or his/her representative will explain the nature of the study to the subject, and answer all questions regarding this study.

Has been changed to read:

The Investigator or his/her representative will explain the nature of the study to the subject. The subject must be able to understand the nature of the study and have the opportunity to have any questions answered by the Investigator.

3.0 Introduction

This statistical analysis plan (SAP) describes the statistical analyses to be completed by AbbVie clinical statisticians for Levodopa-Carbidopa Intestinal Gel (LCIG) Study M15-535 with a protocol dated 26 May 2016 incorporating one amendment (original protocol: 03 May 2016, Amendment 1: 26 May 2016). It provides details to further elaborate statistical methods as outlined in the protocol and describes analysis conventions to guide the statistical programming work.

Unless noted otherwise, all analyses will be performed using SAS version 9.2 or higher (SAS Institute Inc., Cary, NC 27513) under the Unix operating system.

4.0 Study Objectives, Design and Procedures

4.1 Objectives

The primary objective of this interventional study is to examine the effect of LCIG treatment relative to that of Optimized Medical Treatment (OMT) on dyskinesia as measured by the Unified Dyskinesia Rating Scale (UDysRS) Total Score.

The Secondary objective is to assess the effect of LCIG treatment relative to that of OMT on dyskinesia as measured by PD Diaries, motor symptoms, motor complications, health-related outcome measures, safety and tolerability.

4.2 Design Diagram

This is a Phase 3b, open-label, randomized multicenter 12 week study assessing the efficacy of LCIG treatment compared to OMT on dyskinesia in subjects with Advanced Parkinson's Disease.

The study will consist of three sequential parts:

Part 1: Screening period. The screening period will consist of three visits, Visit 1 (V1), Visit 2 ([V2] [optional]) and the Randomization Visit (V3) in which the subject will be

assessed to determine eligibility. The duration of the Screening Period will be between 30-67 days to accommodate the required procedures, training and collection of diaries, and to allow for stabilization of anti-PD medications and medications to treat dyskinesia. All anti-PD medications and medications to treat dyskinesia are required to be stable for a minimum of 30 days prior to randomization.

Part 2: Treatment period. Those subjects randomized to OMT at the end of V3 will remain on their current optimized anti-PD regimen. The day after randomization will be considered Day 1 of their treatment period and subjects will have study visits at the end of Weeks 2, 4, 8, and 12. Subjects randomized to LCIG treatment must discontinue all other anti-PD medications other than amantadine (e.g., dopamine agonists, COMT-inhibitors, MAO-B inhibitors, anti-cholinergics, and subcutaneous apomorphine, etc.) prior to LCIG treatment initiation on Day 1 (V4); these medications should be tapered off within 14 days after randomization according to the discretion of the Investigator. With the exception of apomorphine, levodopa containing formulations or amantadine, these medications may be restarted if indicated by the subject's individual condition, but not within the first 28 days after LCIG treatment initiation. Optional nasojujunal (NJ) and/or percutaneous endoscopic gastrostomy with a jejunal tube (PEG-J) placement will then be placed. After that, the subject may begin initiation and titration of LCIG infusion to be adjusted to obtain the optimal clinical response in 14 days. The day of initial NJ or PEG-J placement will be considered Day 1 for subjects in the LCIG group. Study visits happen at the end of Weeks 2, 4, 8, and 12.

Characterization Carbidopa Intestinal Gel (LCIG) M15-535 - Statistical Analysis Plan Version 1.0 - 21 May 2018

[figure not shown]

Figure 1. **Study Design Schematic**

Part 3: Follow-up period. The OMT subjects will not have a follow-up visit (V9). Study subjects in the OMT group who complete participation in the study are eligible to transition to commercial LCIG after end of study procedures if judged appropriate by their personal physician. For LCIG subjects who elect to discontinue LCIG and not continue with commercially available product, a V9 will be conducted 1 week after PEG-J removal and the SAE/AE follow-up period will be up until 30 days after PEG-J removal. For LCIG treatment subjects who will transition to commercial product, the SAE/AE followup period will be up until 30 days after the transition. For study subjects in the LCIG group who complete participation in the study and will continue to receive LCIG, subjects will return every 6 weeks to return used LCIG cassettes and be dispensed cassettes. Additional visits every 12 weeks from Week 12 will be scheduled to monitor subject safety and allow for drug resupply until the subject transfers to commercial LCIG.

4.3 Sample Size

Approximately 60 subjects will be enrolled into the study and randomized in a 1:1 ratio to either optimized medical treatment (OMT) or LCIG treatment. Subject randomization will be stratified by country. For sample size determination, it is assumed that the difference of improvement is 10 points on UDysRS total score between the LCIG treatment group and OMT group based on results reported by Pahwa et al (2015). The pooled standard deviation is assumed to be 12 based on results reported by Goetz et al (2013). Assuming that the treatment group difference is 10 points and the pooled standard deviation is 12, 27 subjects per group will have 85% power to declare statistical significance on the primary endpoint at a two-sided significance level of 0.050 based on calculations using nQuery + nTerim 4.0. It is further assumed that 10% of randomized subjects in either treatment group will not provide post-randomization efficacy assessment. Therefore the total planned enrollment is decided to be approximately 60 subjects.

4.4 Interim Analysis

After all randomized subjects have completed the 12-week Treatment Period, or have discontinued during the Treatment Period and those randomized to LCIG have completed Follow-up Period, the primary objective of the study will have been fulfilled. A database lock will occur. Primary analyses of efficacy and safety data comparing LCIG and OMT arms will be conducted at that time.

4.5 Efficacy and Health-Related Outcome Measures

4.5.1 Motor Symptoms/Motor Complications

Motor symptoms will be assessed by the following measures.

- Unified Dyskinesia Rating Scale (UDysRS)
- Parkinson's Disease Diary (PD Diary): normalized average daily hours of OFF time, ON time with troublesome dyskinesia, ON time without troublesome dyskinesia

- Unified Parkinson's Disease Rating Scale (UPDRS) Part III
- Modified Abnormal Involuntary Movement Scale (mAIMS)

4.5.2 Health-Related Outcomes

Health-related outcomes will be assessed by the following measures.

- UPDRS Part II
- Parkinson's Disease Questionaire-8 (PDQ-8)
- King's PD Pain Scale
- Clinical Global Impression of Severity (CGI-S)
- Clinical Global Impression of Change (CGI-C)

A description of each measure is included in Protocol Section 5.3.1.1 Study Procedures. Each measure will be assessed at the times indicated in the relevant study activities flow chart (Appendix A).

4.6 Safety Measures

Safety and tolerability over the course of the study will be assessed by the following measures.

- Adverse event monitoring
- Neurological exams
- Clinical laboratory evaluations
- Electrocardiogram
- Vital signs and weight
- Columbia Suicide Severity Rating Scale (C-SSRS)
- Minnesota Impulsive Disorders Interview (MIDI)
- Sleep Attacks Questionnaire (SAQ)

A description of each measure is included in Protocol Section 5.3.1.1 Study Procedures. Each measure will be assessed at the times indicated in the study activities flow chart (Appendix A).

5.0 **Analysis Populations**

Analyses will be performed utilizing the following datasets.

Intent-to-Treat Dataset

The intent-to-treat dataset will include all subjects who are randomized to the optimized medical treatment, and all subjects who are randomized to LCIG and received at least one dose of study drug following PEG-J placement. The intent-to-treat dataset will be used to summarize efficacy and health outcome measures.

Safety Dataset

The safety dataset will include all subjects who are randomized to the optimized medical treatment, and all subjects who are randomized to LCIG and have a study device (NJ and/or PEG-J) placement procedure. The safety dataset will be used to summarize safety data during the OMT and LCIG treatment period.

6.0 **Analysis Conventions**

6.1 **Statistical Significance**

This is a randomized open-label study. Unless otherwise specified, statistical tests will be two-sided and the null hypothesis will be rejected at the significance level of $\alpha = 0.050$. *P* values will be rounded to three decimal points before assessing statistical significance. If the primary efficacy variable UDysRS total score is statistically significant, each of the secondary efficacy variables will be tested using the fixed sequence below as a gatekeeping procedure and at α level of 0.050. Testing will cease at the point that a secondary variable fails to demonstrate statistical significance.

"ON" time without troublesome dyskinesia as measured by the PD Diary

- Parkinson's Disease Questionaire-8 (PDQ-8) summary index
- Clinical Global Impression of Change (CGI-C) Score
- UPDRS Part II Score
- "OFF" time as measured by the PD Diary
- UPDRS Part III Score

6.2 Definition of Study Epochs and LCIG Treatment Period Reference Variables

The following study epochs have been defined to track each subject's progression from screening through study completion or premature discontinuation.

Epoch Name	Epoch Description
Pre	
Device Before (LCIG group only)	
Open	
Transition (LCIG group only)	
Device After (LCIG group only)	
Off	

For subjects in the LCIG group, the date and time of the earliest LCIG tube placement (NJ or PEG-J) recorded on the Device Information eCRF will be considered the treatment start reference date (REFDT) and time (DMREFTM). The date of the last LCIG tube removal, or the date of the last LCIG infusion if there is no device removal will be considered the end of the LCIG treatment period and the following day will be the post-treatment start reference date (REFEDT). For subjects in the OMT group, the date after randomization will be considered the start of treatment period and will be the treatment start reference date (REFDT). The date of the final visit will be considered the end of the OMT treatment period and the following day will be the post-treatment start reference date (REFEDT).

Study Days will be calculated based on the treatment start reference date (REFDT). For time points before REFDT, the Study Day = time point - REFDT. For time points on or after REFDT, the Study Day = time point - REFDT + 1. Thus, the Study Day is a negative value when the time point of interest is prior to REFDT and the Study Day is a positive value when the time point of interest is on or after REFDT. There is no Study Day 0. The Study Day will be labeled as Rx Day on the data listings. RxEnd Day is calculated for each post-treatment time point as the number of days between REFEDT and the specific time point: RxEnd Day = date of time point - REFEDT + 1.

6.3 **Definition of Baseline and Final Observation**

Baseline for PD Diary variables will be the average of the last 3 valid diaries completed on or before the day of randomization. Baseline for all efficacy, health outcome and safety measures, other than the PD Diary, will be defined as the last non-missing observation that is on or before the day of randomization.

The final visit for PD Diary variables for the OMT group will be the average of the last 3 valid diaries that are after the day of randomization during the 12-week Treatment Period. The final visit for PD Diary variables for the LCIG group will be the average of the last 3 valid diaries that are after the date of the first LCIG infusion following PEG-J placement and on or before the date of the last LCIG infusion during the 12-week

Treatment Period. The final visit for efficacy and health outcome measure, other than PD Diary variables, for the OMT group will be defined as the last non-missing observation that is after the day of randomization during the 12-week Treatment Period. The final visit for efficacy and health outcome measures, other than PD Diary variables, for the LCIG group will be defined as the last non-missing observation that is after the date of the first LCIG infusion following PEG-J placement and no more than 1 day after the last LCIG infusion during the 12-week Treatment Period.

For subjects who discontinue LCIG treatment during the 12-week Treatment Period or complete the 12-week Treatment Period but not going to transit to commercial product, the final visit for safety assessments will be defined based on the final removal of all LCIG devices and will be the last non-missing observation that is after the date and time of the first LCIG tube (NJ or PEG-J) placement procedure and no more than 1 day after the final removal of all LCIG tubes. For subjects who transit to commercial product, the final visit will be the last non-missing observation during the 12-week Treatment Period in the database. Safety assessments on the date of the first PEG-J placement procedure that do not have a time of assessment or sample collection recorded will be assumed to be post-procedure. For subjects in the OMT group, the final visit for safety assessments will be defined as the last non-missing observation that is after the day of randomization during the 12-week Treatment Period.

6.4 Analysis by Planned Visit for PD Diary Variables

The PD Diary will be used by the subject and/or their caregiver to record parkinsonian symptoms on the 3 days prior to clinic visits as indicated in the Schedule of Study Activities. The total daily awake time will be calculated for each diary as described in Section 9.4. Only diaries with at least 12 hours of awake time will be considered valid and included in the analyses.

The PD Diary is planned to be completed on each of 3 days prior to selected scheduled visits. It is expected that all 3 diary days will fall in the same visit window as long as the subject is on schedule. However, there may be rare instances where the timing of a

subject's visit schedule shifts due to unforeseen circumstances. To ensure that each adjacent diary day will be assigned to the same visit window, each diary day will be linked to the nearest scheduled visit that occurred after the date on which the diary was completed. The PD diary data will be assigned to a visit window based on the date of this scheduled visit.

Assessment	Planned Visit	Nominal Study Day	Study Day Range ^a
PD Diary	Baseline		\leq date of randomization
	Week 2	14	2 - 21
	Week 4	28	22 - 42
	Week 8	56	43 - 70
	Week 12	84	≥ 71

For subjects in LCIG group, all post-baseline PD Diaries must also be after start of LCIG infusion through PEG-J and on or before the date of the last LCIG infusion in the 12-week Treatment Period.

The valid diary days (at least 12 awake hours) will be used to compute the average daily times. For post-baseline visits, the valid diary days must be within 7 days of the scheduled visit but not on or after the day of the scheduled visit. If more than 3 valid diary days are available, the last 3 days in each visit window will be used. If only 1 or 2 valid diary days are available prior to a scheduled visit, data from the available days will be used to calculate the average daily times. Subjects that do not have any valid diary days for a visit will have the average daily times set to missing for that visit.

6.5 Analysis by Planned Visit for Non-Diary Variables

A midpoint convention will be used to assign all observations to a planned visit based on the Study Day of the observation. If there are multiple observations on the same day, the average will be taken and considered the observation for the day. If more than one observation is assigned to a planned visit, the last observation will be selected and considered the observation for the planned visit.

The following Study Day windows will be used to assign efficacy and health outcome assessments to planned study visits during the 12-week Treatment Period. Assessments

on the day of first day of LCIG infusion via PEG-J are not planned and will not be included in the analysis.

Assessment	Planned Visit	Nominal Study Day	Study Day Range ^a
UDysRS, UPDRS,	Baseline		\leq date of randomization
mAIMS, CGI-C	Week 2	14	2 - 21
	Week 4	28	22 - 42
	Week 8	56	43 - 70
	Week 12	84	≥ 71
PDQ-8	Baseline		\leq date of randomization
	Week 8	56	2 - 70
	Week 12	84	≥ 71
King's PD Pain Scale	Baseline		\leq date of randomization
	Week 4	28	2 - 42
	Week 8	56	43 - 70
	Week 12	84	≥ 71

a. For subjects in LCIG group, all post-baseline assessments must also be after start of LCIG infusion through PEG-J and no more than 1 day after the date of the last LCIG infusion in the 12-week Treatment Period.

The following Study Day windows will be used to assign safety assessments during the
12-week Treatment Period to planned study visits.

Assessment	Planned Visit	Nominal Study Day	Study Day Range ^a
Vital signs and weight,	Baseline		\leq date of randomization
MIDI, Sleep Attacks	Week 2	14	2 - 21
Questionnaire, C-SSRS	Week 4	28	22 - 42
	Week 8	56	43 - 70
	Week 12	84	≥ 71
	Week 13 FU ^b	91	$2 \leq RxEnd Days$
Clinical labs and	Baseline		\leq date of randomization
Electrocardiograms, Special labs	Week 8	56	1 - 70
Special laus	Week 12	84	≥ 71

For subjects in LCIG group, all post-baseline assessments must also be no more than 1 day after the final PEG-J a. removal for subjects who do not transit to commercial product or no more than 1 day after the final Study M15-535 LCIG infusion during 12-week Treatment Period for subjects who transit to commercial product.

b. Applicable only to LCIG subjects who will not continue on commercial product.

For LCIG subjects who enter the Transition Period, vital signs and weight, special labs, C-SSRS and MIDI will be assessed every 12 weeks.

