5.1.3 Study Follow-Up

Follow-Up Visit (V9) (LCIG Treatment Subjects Not Continuing on Commercial Product)

[figure not shown]
For LCIG subjects who elect to discontinue LCIG and not continue with commercially available product, a V9 will be conducted 1 week after PEG-J removal and the SAE/AE follow-up period will be up until 30 days after PEG-J removal.

Commercial Transition Visits (LCIG Treatment Subjects Continuing on Commercial Product)

For LCIG treatment subjects who will transition to commercial product, the SAE/AE follow-up period will be up until 30 days after the transition.

Study subjects in the LCIG treatment group who complete participation in the study and for whom continuation of treatment with LCIG is judged appropriate by the Investigator will continue to receive LCIG treatment until transition to commercial product is coordinated with the Sponsor's commercial affiliate.

Upon transfer of subjects to commercial LCIG treatment the monitoring of such therapy will be the responsibility of the subject's personal physician. All necessary support will be provided by the Sponsor's local representative. Follow-up care in these circumstances will be based on the judgment of the subject's personal physician and, following the 30 day SAE/AE follow-up period, no formal collection of data will be conducted except for regular Adverse Drug Reaction (ADR) reporting in accordance with local instructions.

OMT Subjects

The OMT subjects will not have a follow-up visit (V9).

Study subjects in the OMT group who complete participation in the study are eligible to transition to commercial LCIG treatment after end of study procedures if judged appropriate by their personal physician. This transition is not study related.

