10.7 Analysis of Minnesota Impulsive Disorders Interview (MIDI)

The Minnesota Impulsive Disorders Interview (MIDI) will be administered to monitor for the development of intense impulsive behavior. It includes the following modules: buying disorder, kleptomania, trichotillomania, intermittent explosive disorder,

pyromania, pathological gambling and compulsive sexual behavior. A subject's MIDI screen is positive for a module if:

- Buying Disorder: Positive screen if the subject answers "yes" to 1a, 2a, 3a, and 4a
- Kleptomania: Positive screen if the subject answers "yes" to 1a, 2a, 3a, and 4a
- Trichotillomania: Positive screen if the subject answers "yes" to 1, 3, 4a, 5, and 6
- Intermittent Explosive Disorder: Positive screen if the subject answers "yes" to 1a, 1b, 1c, and 1d; in addition, the subject must answer "no" to 1f
- Pyromania: Positive screen if the subject answers "yes" to 1a, 2, 3, 4, and 5; in addition, the subject must answer "no" to 1b, 1c, 1d, and 1e
- Pathological Gambling: Positive screen if the subject answers "yes" to 1, and to at least 5 of the rest of the questions
- Compulsive Sexual Behavior: Positive screen if the subject answers "yes" to 1, 2a, 3a, or 4a

Positive screens on the MIDI will be summarized for the study period on or before the date of randomization and during the 12-week Treatment Period. Each summary will include the number and percentage of subjects in each treatment group with a positive screen for each MIDI module as well as for any of the MIDI modules.

A summary of the number and percentage of subjects with a positive screen for each MIDI module as well as for any of the MIDI modules during the Transition Period will also be provided for LCIG subjects who enter the Transition Period.

A listing will also be prepared that includes all subjects with 1 or more positive screens for any of the MIDI modules.

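### In SAP 6.5, note a contradicts the Week 13 follow-up row, so V9 cannot be assigned to its own planned visit once a PEG-J has been removed

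*SAP*

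**What the plan says.** Four statements have to be read together.

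- **End of treatment and RxEnd Day (SAP 6.2).** The LCIG treatment period ends on "The date of the last LCIG tube removal, or the date of the last LCIG infusion if there is no device removal". REFEDT is the day after that, and "RxEnd Day = date of time point - REFEDT + 1".
- **Week 13 FU row (SAP 6.5, safety windows).** Nominal Study Day 91, range RxEnd Day 2 or later. Note b: "Applicable only to LCIG subjects who will not continue on commercial product".
- **Note a (same table, attached to the header of the range column).** For LCIG subjects not moving to commercial product, "all post-baseline assessments must also be no more than 1 day after the final PEG-J" removal. The note does not exempt the Week 13 row.
- **Timing of V9 (Protocol 5.1.3).** For LCIG subjects who stop and do not continue on commercial product, "a V9 will be conducted 1 week after PEG-J removal". Protocol Table 4 lists vital signs and weight, MIDI, C-SSRS and the sleep attack questions at V9.

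SAP 6.3 applies a similar limit to the final safety visit but words it by all tubes: "no more than 1 day after the final removal of all LCIG tubes".

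**The concern.** Note b restricts the Week 13 row to the same subjects for whom note a sets its limit at PEG-J removal. If one rule starts after the other ends, the row stays empty for every subject with a PEG-J removal, although V9 is the visit it was written for. V9 vital signs and weight would then belong to no planned visit, and only values meeting the PCS criteria would reach an output the SAP describes, namely the listing in 10.4.3. Orthostatic hypotension is among the important identified risks in Protocol 3.2, and weight loss is an adverse event of special interest, so a post-removal reading of these measures is worth tabulating.

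The wording also leaves a programmer to choose a remedy, and one obvious choice (dropping note a) produces a different error, shown in the working.

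**Working it through.** **Inputs.** End of treatment for a subject with a tube removal: removal date R. REFEDT = R + 1. Window for Week 13 FU: RxEnd Day ≥ 2. Note a: date ≤ R + 1, taking the PEG-J as the last tube out. V9: R + 7, or R + 4 to R + 10 with the protocol's ±3-day visit window.

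**Plan's own figure.** Nominal Day 91: if removal falls on Day 84 (Week 12), 84 + 7 = 91. This reproduces.

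**RxEnd Day in terms of removal.** RxEnd Day = date − (R + 1) + 1 = date − R, that is, days since removal.

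| Observation | RxEnd Day | Meets Week 13 row (≥ 2) | Meets note a (≤ R + 1) |
|---|---|---|---|
| R + 1 | 1 | no | yes |
| R + 2 | 2 | yes | no |
| R + 4 | 4 | yes | no |
| R + 7 (V9) | 7 | yes | no |
| R + 10 | 10 | yes | no |

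The row needs date − R ≥ 2 and note a needs date − R ≤ 1, so no date meets both. Checking removal Days 1 to 120 against observation dates from R − 30 to R + 60 also gives 0 dates.

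**What is lost and what is kept.** Suppose the last infusion is on Day 40 and the PEG-J comes out on Day 54. Observations on Days 41 to 55 satisfy note a and stay in the on-treatment windows. Those from Day 56 onward do not, including V9 on Day 61 (61 − 54 = RxEnd Day 7).

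**If note a were simply deleted.** V9 would also satisfy an on-treatment window:

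- removal Day 20: V9 on Day 27, Week 4 (22–42)
- removal Day 40: V9 on Day 47, Week 8 (43–70)
- removal Day 84: V9 on Day 91, Week 12 (≥ 71, no upper bound)

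SAP 6.5 takes the last observation assigned to a planned visit, so in the third case V9 would replace the Week 12 value, in the LCIG arm only.

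**If note a is kept on Weeks 2 to 12 only.** On-treatment rows run to RxEnd Day 1 and follow-up starts at RxEnd Day 2. The two meet with no gap and no overlap, and V9 falls in its own row.

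**The case against.** The best defence is that the intention is plain. The limit of RxEnd Day 1 and the start at RxEnd Day 2 are exact complements, and the Week 13 row has its own units and its own note. Note a was very probably meant for the on-treatment rows alone. V9 is also LCIG-only, with no OMT comparator, so its data are descriptive. This settles the severity. It does not remove the conflict, because the written rule still gives an empty row and the SAP should not rely on the programmer to guess its scope.

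Several stronger readings are tempting, and the documents do not support them.

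- *The row can never hold an observation.* Not so where no PEG-J was removed (NJ only, or tube left in place). Note a then has no anchor date, while RxEnd Day still counts from NJ removal or last infusion.
- *Safety data after stopping LCIG are lost.* The limit runs from tube removal, not from the last infusion.
- *V9 is the only safety visit after stopping.* Protocol 5.4.1 asks for the Week 12 assessments as soon as possible after withdrawal once the PEG-J procedure has begun. Done by removal + 1 day, these satisfy note a.
- *A planned Week 13 table comes out blank for all four measures.* The window table and the vital-sign summaries in SAP 10.4.1 are framed by the 12-week Treatment Period, and no Week 13 table is described. MIDI is summarised by period: "Positive screens on the MIDI will be summarized for the study period on or before the date of randomization and during the 12-week Treatment Period". Sleep attacks and C-SSRS (10.6, 10.8) are also by period. Those two sections refer both to Day 1 onward and to the 12-week period, so whether they include V9 is unclear, but this window does not decide it.
- *Adverse events or alerts are missed.* TEAEs run to 30 days after tube removal (10.2). The PCS listings and the listings of positive MIDI, C-SSRS and sleep attack responses do not depend on this table.
- *Leaving V9 out of the final safety visit is a further loss.* That is an on-treatment rule by design. Protocol 8.1.1 likewise limits the final evaluation to shortly after the end of treatment.

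**Conclusion.** The contradiction is real for any LCIG subject who has a PEG-J removal and does not move to commercial product. For that subject every V9 observation, at RxEnd Day 7 (4 to 10 with the visit window), falls outside the only planned visit meant for it.

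The consequence is minor. What is lost is the visit assignment of data from removal + 2 days onward, in practice V9, and the by-visit effect falls on vital signs and weight. As the SAP is written, no efficacy result, between-group test or adverse event count changes.

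The number of subjects affected is not given. It is some part of the approximately 30 randomised to LCIG. The conclusion assumes that note a applies to every row under the header it is attached to, and that the PEG-J is the last tube removed.

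**What to change.** In SAP 6.5:

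1. State that note a applies to the Week 2 to Week 12 rows and not to Week 13 FU. Keep it on those rows, so that V9 cannot drift into an on-treatment window, above all the open-ended Week 12 window (Study Day 71 or later).
2. Tie note a to final removal of all LCIG tubes instead of final PEG-J removal, matching SAP 6.3. This also supplies a cut-off for subjects who stop during the NJ phase.

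In SAP 10.4, say that V9 vital signs and weight are presented as a descriptive, LCIG-only post-treatment column. Similar V9 columns for MIDI and C-SSRS are optional.

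The cost is a footnote edit and one descriptive column. No new data are needed and no test is added.
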